11.2.3 Tolerability of treatment

All randomised participants will be included in this analysis. Comparison of the frequency of treatment withdrawal because of suspected intolerance between the aspirin group and the placebo group will be tested using Chi-square statistics. The number of participants discontinuing treatment prematurely for any reason will be summarized by treatment group and by reasons for discontinuation. The incidence of all suspected adverse treatment reactions will be summarized by treatment group.

11.2.4 Procedures to account for missing data

For the main analyses, all participants lost to follow-up will be presumed to have an ulcer that remained unhealed.

12. Ethical Approval and Informed Consent

12.1 Ethics Committee

Ethical approval of the trial protocol and protocol-related documents will be sought from a Health & Disability Ethics Committee.

12.2 SCOTT Committee

No New Zealand manufacturer currently produces a 150 mg dose of aspirin. Therefore Medsafe have advised approval for an exemption for clinical trial of a new medicine under s30 of the Medicines Act is required. Section 30 clinical trial exemption was obtained in October 2014 (TT50-5199 (1700)). Optimus Healthcare Ltd will be the compounding pharmacy for the trial. The company meets the GMP requirements for Medsafe in New Zealand and has been involved in preparation of medicines for other trials.

12.3 Informed Consent

District nurses will screen patients for potential participants. If a patient expresses interest in participating in the trial, the district nurse will obtain verbal consent to forward the patient's name and telephone number to the Research Nurse. After contact by the Research Nurse, if the patient wishes to participate in the trial, Visit 1 will be arranged and informed consent will be obtained during that visit if the patient wishes to participate in the trial.

13. Adverse Event reporting

13.1 Definition of an adverse event

An adverse event (AE) is any untoward clinical occurrence in a participant and does not necessarily have a causal relationship with the treatment. An AE can therefore be any unfavourable and unintended sign, symptom, or disease temporally associated with the use of trial treatment, whether or not it is considered related to the product. In this trial an AE will include any illness, sign, symptom, or clinically significant abnormality that has appeared or worsened during the course of the clinical trial, regardless of causal relationship to the treatment(s) under trial.

13.2 Notification of adverse events

During the trial information about AEs will be sought at the 6 month trial follow-up visit by the research nurse. AEs reported from the district nursing service or other health practitioners should be reported on a CRF X as soon as possible after notification.

AE data will be aggregated and reported by the trial statistician at intervals specified by the Data Safety Monitoring Board (DSMB).

Serious adverse events

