6.1 Recruitment source & process

Patients with venous leg ulcers who present for treatment to or already receiving treatment from the community-based district nursing services at trial centres previously involved in the National Institute of Health Innovation's (NIHI) leg ulcer trials will be recruited. These centres are based within Auckland, Counties Manukau, Waikato, and Southern District Health Boards, and Nurse Maude community nursing services in Christchurch. The same model of recruitment is used as was successfully employed in previous venous leg ulcer trials in New Zealand (figure 4). A 0.5 FTE Research Nurse will be seconded to the trial from each trial centre (employing authority will be reimbursed).

The District Nurse will identify potential participants, obtain verbal consent from them to be contacted by the Research Nurse if the patient is interested in the trial and notify the research nurse at each trial centre. The Research Nurse will screen the patients for eligibility. Eligible patients will be consented, assessed, and randomised by the Research Nurse at a location convenient to the patient. The location may be a clinic, the patient's home or workplace. Once randomised, the participant will receive the allocated treatment from the Research Nurse, who will also conduct the endpoint visits at 24 weeks after randomisation, again at a location convenient to the participant. In between Research Nurse visits the participants will continue to receive normal care by the District Nurses.

[figure not shown]

Figure 3: Flow chart of proposed study.

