9.1 Primary outcome measure

Time to complete healing (defined as intact skin without a scab) is recommended as an outcome to be included in research by the Cochrane Collaboration Wound Review Group and a 24 week follow up period is considered a minimum. Time to event data will be obtained from clinical records. District nurses visit patients on a weekly basis as part of normal care and record healing (average number of district nurse visits was 1.1 per week in the HALT trial). At 24 weeks, the Research Nurse will determine if the reference ulcer is healed. If the reference ulcer is healed, the research nurses will access clinical records to determine the date of healing was first reported during the 24-week period. If the reference ulcer is unhealed, the Research Nurse will determine from the clinical record whether the reference ulcer had healed at any time prior to 24 weeks. If there is no mention of healing then the ulcer will be assumed to have been unhealed during the 24 weeks. If the reference ulcer is recorded as healed during that time, the unhealed ulcer will be assumed to be a recurrent ulcer and the date healing is first recorded will be assumed to be the healing date.

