9.2 Secondary outcome measures

The following secondary outcome measures will be assessed in all participants at 24 weeks after randomisation:

- Proportion of participants with a healed reference VLU at 24 weeks.

- Estimated change in ulcer area – obtained from measuring maximum width and length of reference ulcer at baseline and endpoint and the ulcer area at each time point estimated using the calculation for area of an ellipse.⁵⁰ See rationale above for not using more complex methods of ulcer measurement.
- Change in HRQoL: Measured at baseline and at 24 weeks. Each person's perception of his or her general health will be assessed using the RAND 36-item Health Survey (a version of SF-36), EQ5D and ulcer-related health using the CXVUQ.^{51,52} The EQ5D and SF-36 are well-validated questionnaires for assessing quality of life in New Zealand and generating utility values for economic analyses.^{53,54 55,56} However, they may not be as responsive as a disease-specific instrument to changes in ulcer state (healed *versus* unhealed) over the short-term.^{22,57} Consequently, the CXVUQ will also be used, as it has been found to be very responsive to changes in VLU healing state.²²
- Adverse events: Measured throughout the 24-week follow up. Standard definitions of adverse events will be used and adverse events reports will be reviewed by one of the medically-qualified co-investigators and coded using the ICD-10 AM. All participants will be issued with a Clinical Trial Card, stating their participation in the trial and the possibility they are receiving low dose aspirin. If the participant presents with signs and symptoms of a serious adverse event, such as myocardial infarction, stroke, or extra-cranial bleed, the Clinical Trial Card will recommend they discontinue trial treatment and appropriate treatment initiated. These participants will still be included in follow up at 24 weeks.
- Treatment adherence: Measured at 24 weeks by count of remaining capsules by the Research Nurse.
- Efficacy of blinding: Measured at 24 weeks, the efficacy of blinding will be tested by asking patients which treatment they believed they received, and asking the same question of the research nurses.

10. Data collection and follow-up

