10.2 Schedule of trial visits and procedures

	Visit 1	Phone/email contact	Visit 2	District Nurse	Visit 3 Research Nurse
Timing	Week -1	Week-1 to 0	Week 0	Weeks 1-24	Week 24
Case Record Form	A		B	X	E
General data					
Eligibility criteria	X		X		
Age & sex	X				
Ethnicity	X				
Informed consent	X				
Clinical history	X				
Record or obtain ABI	X				
Confirm safety with GP		X			
Confirm with participant visit 2		X			
Clinical information					
Concomitant medications			X		X
Compression system			X		X
Ulcer measurement (max W x L)			X		X
Other data collection					
Quality of life measures			X		X
Adverse events				X	X
Pill count					X
Testing blinding					X
End of trial participant survey					X
Treatment allocation					
Trial medication			X		

Form X will be completed by Research Nurse, but Research Nurse may be notified by District Nurse of possible adverse event.

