11.2.2 Treatment effect

All data analyses will be carried out on an intention-to-treat basis⁶³. Time-to-event data will be analysed using Kaplan Meier plots and log rank test, and Cox regression will be used to take into account known covariates and the varying times since randomisation. The assumption of proportionality will be checked using standard graphical techniques. Simple incidence rates, relative risks, absolute risks and numbers needed to treat, and 95% CIs will be obtained for all binary outcomes in the first instance, with subsequent multiple logistic regression analysis conducted if necessary to adjust for imbalance in covariates. Continuous outcomes will be analysed using multiple linear regression and adjusted for baseline value and other covariates if needed. Adverse events will be analysed using incidence rate ratios. A *kappa* will be calculated for the evaluation of the efficacy of blinding. Should aspirin prove effective in the primary analysis, heterogeneity of effects on time to healing will be analysed using subgroups specified *a priori* in the Statistical Analysis Plan.

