14.5 Treatment on completion of trial

Participants will be asked to return all unused aspirin capsules to the research nurse. Returned capsules will be disposed of at the end of the trial follow-up period by the Research Nurse in accord with local DHB protocol.

15. Relevance to Health

The trial contributes to the goal of improving outcomes for individuals and populations with disease as follows:

- *More people could be healed* - Even with good compression 30-60% of patients remain unhealed after 12 weeks of compression therapy in clinical trials.²⁴⁻²⁷ New Zealand trials suggest a baseline healing rate of 50% at 12 weeks and aspirin could increase this proportion to 65% at 12 weeks and 75% at 24 weeks.
- *Improved quality of life* - Ulcer healing improves quality of life,²² and earlier healing will increase patients' quality of life, especially in the older people who more commonly have leg ulcers.

The trial also contributes to the goal of cost-effective sustainable solutions as follows:

- *Reduced costs* - The average cost of 12 weeks venous ulcer treatment is NZ\$972, a figure inflated by patients that remain unhealed. The average cost of healed patients for a 12-week period is NZ\$535 compared to NZ\$1405 for those that remain unhealed.⁸ Increasing the number of patients healed early will decrease the overall spend on this patient group.
- *Reduced burden on district nursing services* - As people's ulcers heal they no longer need district nursing and other related services for leg ulcer management, freeing up these resources.
- *Easier access to a low cost, effective adjuvant* - Aspirin is a safe, inexpensive, over-the-counter medication, with very few barriers to patient use or practitioner recommendation.

16. Dissemination of Results

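### Between randomisation and week 24 adverse events are captured only passively, through contact that falls away at healing, so a faster-healing arm may have its events under-counted

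*Protocol*

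**What the plan says.** Protocol 9.2 sets the window: "Adverse events: Measured throughout the 24-week follow up". Section 13.2 provides one active enquiry: "During the trial information about AEs will be sought at the 6 month trial follow-up visit by the research nurse". For the months before it, 13.2 relies on notification: "AEs reported from the district nursing service or other health practitioners should be reported on a CRF X as soon as possible after notification".

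The schedule in 10.2 marks adverse events for weeks 1-24 under the District Nurse and again at Visit 3. Its footnote makes the interim route permissive: "Form X will be completed by Research Nurse, but Research Nurse may be notified by District Nurse of possible adverse event". Section 6.1 puts no research nurse contact in between: "In between Research Nurse visits the participants will continue to receive normal care by the District Nurses". Section 9.1 describes district nurse visits as about weekly, noting that the "average number of district nurse visits was 1.1 per week in the HALT trial".

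Section 15 (Relevance to Health), arguing for reduced service burden, says that as people's "ulcers heal they no longer need district nursing and other related services for leg ulcer management". On analysis, 11.2.2 says only: "Adverse events will be analysed using incidence rate ratios". It does not state the person-time, or how events from different sources are handled.

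**The concern.** While the ulcer is open, a nurse sees the participant about once a week and can pass on an event. After healing no scheduled contact replaces those visits until week 24. A later event is then recorded only if another practitioner gives notice or the participant recalls it at week 24. Detection may therefore depend on healing, which the trial drug is meant to bring forward.

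Blinding does not protect against this, because the contact follows the state of the ulcer and not knowledge of allocation. It is also a separate matter from whether the participant is still taking capsules, and it affects events unrelated to the drug.

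If aspirin works, any such bias makes it look safer, and more so the better it works. That matters here because 2.7 gives the need for more risk/benefit evidence in the oldest patients as a reason for not excluding them.

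**Working it through.** The Protocol gives no figure for capture by either route, so there is none to reproduce. The check bounds the effect from the design assumptions.

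**Inputs**
- Control median time to healing: 92 days (11.1).
- Design difference: four weeks, so the aspirin median is 92 − 28 = 64 days (11.1). Check: 92/64 = 1.4375, against the stated hazard ratio of 1.45.
- Window: 24 weeks = 168 days (9.2).
- Visit rate: 1.1 per week (9.1).
- Assumed: constant healing hazards; contact ends when the reference ulcer heals; a constant event rate; full capture before healing; a share r of events captured after healing. The value of r is not documented, so the range 0 to 1 is shown.

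**Step 1: time under nurse contact**

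Mean days = (1 − exp(−λ × 168))/λ, with λ = ln 2/median.
- Placebo: λ = 0.00753, healed by day 168 = 71.8%, mean = 95.3 days (57% of 168).
- Aspirin: λ = 0.01083, healed by day 168 = 83.8%, mean = 77.4 days (46% of 168).

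At 1.1 visits per week this is 95.3/7 × 1.1 = 15.0 visits against 77.4/7 × 1.1 = 12.2. The contact ratio is 77.4/95.3 = 0.81. With the hazard ratio of 1.77 that 11.1 cites from the earlier cohort, the aspirin mean is 67.0 days and the contact ratio is 0.70.

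**Step 2: observed ratio when the true ratio is 1**

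Mean days after healing are 168 − 77.4 = 90.6 (aspirin) and 168 − 95.3 = 72.7 (placebo). The observed ratio is (77.4 + r × 90.6)/(95.3 + r × 72.7).

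| r | Observed ratio |
|---|---|
| 1 | 1.00 |
| 0.8 | 0.98 |
| 0.6 | 0.95 |
| 0.4 | 0.91 |
| 0.2 | 0.87 |
| 0 | 0.81 |

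**Step 3: observed ratio when there is a real excess on treatment**

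The synopsis (Duration of Treatment) has treatment last less than 24 weeks if the ulcer heals. Take an illustrative excess of 1.25, present only on treatment, with treatment stopping at healing. The true ratio over the whole window is (1.25 × 77.4 + 90.6)/168 = 1.115. The observed ratio is (1.25 × 77.4 + r × 90.6)/(95.3 + r × 72.7).

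| r | Observed ratio | Relative to 1.115 |
|---|---|---|
| 0.6 | 1.09 | 2% lower |
| 0.4 | 1.07 | 4% lower |
| 0.2 | 1.05 | 6% lower |
| 0 | 1.02 | 9% lower |

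**The case against.** The strongest reply is that the week-24 enquiry reaches every participant, healed or not, and can recover events that were never notified. That stands as a limit on the size: at full recovery the bias is nil. It does not remove the concern, since the enquiry relies on recall over up to 24 weeks, and minor events are the most exposed. Serious events are likelier to come to light at week 24 or through other practitioners, whom 13.2 also names.

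The sentence in section 15 is a service-cost argument, not a trial procedure, and it concerns leg ulcer care only. A participant may have several ulcers (10.1) or a recurrence (9.1), which keeps or restores contact. So the 95.3 and 77.4 days are a simplification that probably overstates the gap. The footnote in 10.2 also leaves open that the district nurse route contributes little.

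Three stronger readings are tempting, but the documents do not support them:
- **Under-counting is certain.** No capture share is given, and nothing differs between arms unless aspirin speeds healing.
- **Section 11.2.2 pools both sources over 24 weeks.** It names only the measure. The 24-week window comes from 9.2, and analysis detail is left to the statistical analysis plan.
- **A true ratio of 1.25 falls to 1.02.** Multiplying 1.25 by 0.81 assumes that the drug excess continues after healing, which does not fit the treatment duration in the synopsis. On that duration the true whole-window ratio is already about 1.12.

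The point is still not one that the analysis plan can settle alone. Events cannot be separated by source or onset afterwards unless the form records both.

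**Conclusion.** The concern holds as a possibility with a known direction and a bounded size. Interim capture is passive, the main regular contact falls away at healing, and a faster-healing arm may therefore have events under-counted. Under the design medians it has about 19% less nurse contact. With no true difference the observed ratio lies between 0.81 and 1.00. For an excess of 1.25 confined to treatment, a whole-window ratio of about 1.12 would read as 1.09 to 1.02 when post-healing capture is 60% to 0%.

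These figures rest on constant hazards, contact ending when the reference ulcer heals, full capture before healing and an undocumented capture share. The low end of each range supposes that week 24 recovers nothing, so it is a bound and not an expectation. As planned, the trial could not tell lower detection from lower risk.

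**What to change.** Keep the all-event comparison over 24 weeks, and make these changes:

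1. **CRF X (10.2, 13.2):** record the source or sources of each event (district nurse, other practitioner, week-24 enquiry) and its onset date.
2. **Visit 3 (10.6, 13.2):** ask every participant the same standard question about the whole period, including events already notified. If those were left out of the week-24 set, the slower-healing arm would lose more events from it and the bias would reverse. The visit list in 10.6 does not show the adverse event enquiry that 10.2 and 13.2 schedule, so the question can be written in there.
3. **Analysis (11.2.2 or the statistical analysis plan):** add two supplementary comparisons: (a) events elicited by the week-24 question in all participants; (b) all events with onset before healing, as a rate over person-time from randomisation to healing or week 24. The healing date is already collected for the primary outcome.

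The cost is two fields, one standard question and two tables, with no extra visits. Neither supplementary comparison should replace the main one: (a) relies on recall, (b) depends on time to healing, which is a post-randomisation outcome, and both are less precise. If all three comparisons agree, differential detection is a less likely explanation of the result. If they disagree, the report should say so.

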13.2.1 Definition of a serious adverse event

An SAE is any untoward medical occurrence that:

- Results in death
- Is life-threatening

NOTE: The term "life-threatening" in the definition of "serious" refers to an event in which the participant was at risk of death at the time of the event; it does not refer to an event which hypothetically might have caused death if it were more severe.

- Requires in participant hospitalisation or prolongation of existing hospitalisation

NOTE: In general, hospitalisation signifies that the participant has been admitted (usually involving at least an overnight stay) to the hospital or assessment ward for observation and/or treatment that would not have been appropriate outpatient setting. Complications that occur during hospitalisation are AEs. If a complication prolongs hospitalisation or fulfils any other serious criteria, the event is serious. When in doubt as to whether “hospitalisation” occurred or was necessary, the AE should be considered serious. Hospitalisation for elective treatment of a pre-existing condition that did not worsen from baseline is not considered an AE.

- Results in persistent or significant disability/incapacity

NOTE: The term disability means a substantial disruption of a person’s ability to conduct normal life functions. This definition is not intended to include experiences of relatively minor medical significance such as uncomplicated headache, nausea, vomiting, diarrhea, influenza and accidental trauma which may interfere or prevent everyday life functions but do not constitute a substantial disruption.

- Is a congenital anomaly/birth defect.
- Other important medical events, that may not be immediately life threatening or result in death or hospitalisation but may jeopardize the participant or may require medical or surgical intervention to prevent one of the other outcomes listed in the above definition.

13.2.2 Notification of serious adverse events

Timely and complete reporting of all SAEs is necessary to identify events that are treatment related or potentially treatment related, thereby allowing: (1) a greater understanding of the overall safety profile of the treatment; (2) appropriate modification of trial protocols; and (3) adherence to regulatory requirements.

SAEs are to be documented on a CRF X and reported to the project manager within one day (24 hours) of detection. Participant deaths or SAEs that occur within 30 days after stopping the trial treatment should also be reported.

All CRF Xs require sign off by the authorised medical practitioner at NIHI who will assess the AE (blinded to treatment allocation) to determine whether the AE is a possible SAE.

If the AE is a possible SAE, the participant will be withdrawn from treatment, the trial treatment collected by the research nurse and the possible SAE will be notified to the participant’s GP.

The Principal Investigator will have the overall responsibility of ensuring that all events are reported to the regulatory authorities in the appropriate timeframes. The project manager will have the responsibility to ensure that SAEs are appropriately monitored and reported. As participants with AEs will not be unblinded during the trial, there will be no expedited reporting on serious suspected adverse drug reactions.

Participants experiencing AEs that cause interruption or discontinuation of trial treatment, or those experiencing SAEs that are present at the end of their participation in the trial will receive follow-up as appropriate, which may involve referral to the participant’s general practitioner.

All AEs will be classified by a medical coder at the NIHI who will be blind to treatment allocation. Standard definitions of adverse events will be used and graded using the Common Terminology Criteria for Adverse Events v3.0.

